**Figure 6-2 QT Prolongation monitoring flow chart**

#### 6.5.4 Hepatic Safety Management

Patients who develop increased transaminase and/or total bilirubin ( $> 2.0 \times \text{ULN}$ ) levels, should be monitored with a second liver function evaluation for confirmation. If confirmed, liver function should be frequently monitored until values return to pre-treatment levels.

If any of the criteria below are observed at any scheduled or unscheduled visit the sponsor should be notified immediately and the Hepatic Safety evaluation, described below, should be performed preferably within 48- hours of awareness of the abnormality:

Patient experiencing

- ALT or AST  $> 3 \times$  ULN and total bilirubin  $\geq 2 \times$  ULN
- ALT or AST  $> 5 \times$  ULN
- total bilirubin  $> 2.0 \times$  ULN

The following should be performed immediately within 72 hours of awareness of the abnormality:

[figure not shown]
- Perform liver-directed medical history and physical examination (i.e. assess occupational hazards, concomitant medications including OTC meds, inter-current illness, etc.)
- Liver function tests: ALT, AST, total bilirubin, (fractionate to direct/indirect bilirubin if total bilirubin is  $> 2.0 \times$  ULN), Albumin, PT, INR, ALP, and GGT.
- Perform hepatitis screen: anti-HAV, IgM (to confirm acute Hepatitis A), HbsAg, Anti-HBc, anti-HCV (if positive, PCR viral load should be assessed), Anti-HEV, ANA antibodies, anti-smooth muscle anti-bodies, CMV and EBV
- Perform abdominal ultrasound (liver and biliary tree)

[figure not shown]
Liver function tests (LFTs) should be monitored every 3-4 days until resolution or return to baseline status.

Patients should be managed according to the LFT algorithm [Figure 6-3](#). Patients may need to be discontinued if the abnormal liver function criteria are met upon LFT retesting (See discontinuation criteria [Section 7.1.2.1](#)). Progress reports of the event should be maintained until resolution or stabilization (i.e. no further elevation after 2 consecutive assessments).

If any of these criteria are met and not confirmed by repeat testing, and the event is considered to be an adverse event by the investigator, the event must be recorded on the Adverse Event eCRF page; if the event is deemed serious by the investigator, then proceed with completing the SAE form. In addition, any significant findings from the physical examination should be recorded on the Adverse Event eCRF page.

All cases confirmed on repeat testing meeting the laboratory criteria defined above, with no other alternative cause for LFT abnormalities identified, should be considered as “medically significant”, thus, meet the definition of SAE ([Section 8.2.1](#)) and reported as SAE using the term “potential drug-induced liver injury”. All events should be followed up with the outcome clearly documented.

**Figure 6-3 LFT Management Algorithm**

## 6.6 Treatment interruption and treatment discontinuation

Patients experiencing unacceptable toxicity (AE grade 3 or higher) that the investigator considers directly attributable to pasireotide should have their dose reduced or should be withdrawn from the study. [Table 6-4](#) should be regarded as a guideline for the treatment of patients experiencing Adverse Events which are judged to be drug related. Any deviation from these guidelines should be discussed and approved by the sponsor.

If patients permanently discontinued from study treatment without completing the full 35 weeks of treatment in the core phase, the patients will be considered as prematurely discontinued from the study.

All patients must have a safety evaluation 28 days after the last dose of study treatment. Patients who do not complete study completions visit will be documented as a protocol deviation. This applies also to patients who discontinue the trial due to withdrawal of consent unless they do not consent to such a visit. Patients lost to follow up should be recorded as such on the CRF.

Adverse events are described as mild (Grade 1), moderate (Grade 2), severe (Grade 3) or life-threatening (Grade 4). Guidelines for treatment of patients experiencing adverse events are indicated below ([Table 6-4](#)).

**Table 6-4 Guidelines for treatment of patients experiencing adverse events**

Patients	Adverse Event	Action
All	AE grade $\leq$ 2 (mild to moderate)	No drug adjustments
	AE grade $\geq$ 3 (severe to life-threatening) and judged as pasireotide-related	Reduce dose of by 0.3mg bid. If AE improves to grade $\leq$ 2 within 1 week, increase dose by 0.3mg bid. If AE recurs at grade $\geq$ 3, reduce dose by 0.3mg bid again and remain at lower dose. If AE does not improve to grade $\leq$ 2 within 1 week on lower dose, reduce dose by 0.3mg bid again if possible. If AE does not improve to grade $\leq$ 2 within 1 week on 0.3mg bid patient should be discontinued from study treatment
	AE grade $\geq$ 3 (severe to life-threatening) and judged as cabergoline-related	Reduce dose from daily schedule to every other day schedule. If AE improves to grade $\leq$ 2 within 1 week, increase dose to daily schedule. If AE recurs at grade $\geq$ 3, reduce dose every other day schedule again and remain at that schedule. If AE does not improve to grade $\leq$ 2 within 1 week on the every other day schedule, patient should be discontinued from study treatment
	All patients	For patients experiencing hyperglycemia, the dose should be reduced if severity grade 3 or greater persists despite appropriate management. If the hyperglycemia is considered to be life-threatening, the patient should be withdrawn from study treatment regardless of anti-diabetes treatment
	AE grade 3 – All patients	NCI-CTCAE v4.03 grades diabetes that is treated with insulin as a grade 3. However, diabetes grade 3 will require a study drug dose reduction only in cases of uncontrolled hyperglycemia despite appropriate management. Patients who despite appropriate therapeutic interventions and dose reduction of study drug, develop uncontrolled diabetes and/or consistently high blood glucose values: FPG $\geq$ 240mg/fdL (13.3 mmol/L) or HbA1c value $\geq$ 10% will require study treatment discontinuation
	Hypocortisolism	If a patient shows high sensitivity to pasireotide 0.6 mg bid resulting in cortisol values $<$ LLN and/or signs/symptoms consistent with the diagnosis of hypocortisolism, the dose of pasireotide can be decreased to 0.3 mg bid. Despite the dose reduction, some patients may still present with cortisol values $<$ LLN and/or signs/symptoms consistent with hypocortisolism; in this case the dose of pasireotide can be further reduced to 0.3 mg qd in order to achieve and maintain normal cortisol levels.
No dose reductions are required in case of a QT prolongation but guidelines for QT monitoring and discontinuation criteria outlined in Section 6.5.3		

## 6.7 Permitted concomitant therapy requiring caution and/or action

Patient must be told to notify the investigational site about any new medications he/she takes after the start of the study drug, as well as any changes in the dose of any medication the patient was taking prior to or during the study. All medications (other than study drug) and significant non-drug therapies (including physical therapy and blood transfusions) administered during the study must be listed on the Concomitant Medications or the Procedures and Significant Non-Drug Therapies CRF, respectively. Diabetic patients must continue their treatment for diabetes throughout the study as indicated. If oral contraception is

used, the patient must have been practicing this method of birth control for at least three months prior to enrollment and must agree to continue the oral contraceptive throughout the course of the study and for 30 days after the last dose of study drug.

#### **6.7.1 Prohibited concomitant therapy**

PRAR $\gamma$  agonists (rosiglitazone or pioglitazone) treatment is not permitted during the study as it could affect patient's ACTH levels. Treatment with prednisolone is prohibited as this interferes with the UFC detection. Use of the medications listed in below that requires a washout are also prohibited during the study.

Further, the use of concomitant medications with a known risk for QT prolongation is prohibited and requires the discontinuation of the patient from the study prior to starting the respective QT prolonging medication. Please refer to [Appendix 4](#) for guidance regarding medications which pose a known risk for QT prolongation.

Patients on medical treatment for Cushing's disease the following washout periods must be completed before screening assessments are performed:

1. Inhibitors of steroidogenesis (ketoconazole, metyrapone): 1 week
2. Pituitary directed agents: Dopamine agonists (bromocriptine, cabergoline) and PPAR $\gamma$  agonists (rosiglitazone or pioglitazone): 4 weeks
3. Octreotide LAR, Lanreotide SR and Lanreotide autogel: 14 weeks
4. Octreotide (immediate release formulation): 1 week
5. Progesterone receptor antagonist (mifepristone): 4 weeks
6. Pasireotide s.c.: 2 weeks
7. Pasireotide LAR: 12 weeks

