## 2.2 Rationale for the study design

This is an open-label, multi-center international non-comparative study with adult patients with confirmed diagnosis of Cushing's disease. The study will consist of patients who have never received pasireotide or patients who have received pasireotide sometimes in the past but was discontinued for reasons not related to safety. The study will also enroll pasireotide-treated patients who at the time of screening have not achieved biochemical control despite maximal tolerated doses of pasireotide for at least 8 weeks.

Pasireotide naïve patients will start pasireotide monotherapy at the dose of 0.6 mg s.c. bid. If at the end of the 8 week treatment period, the biochemical control is not achieved and the 0.6mg bid dose is well tolerated, the pasireotide dose will be increased to 0.9mg bid. If the 0.9mg bid dose of pasireotide does not lead to biochemical control, cabergoline will be added with a starting dose of 0.5mg qd. If the combination dose of 0.9mg bid of pasireotide plus 0.5mg qd cabergoline does not achieve biochemical control, the cabergoline dose will be increased to 1.0mg qd.

Patients who are currently treated with maximal tolerated doses of pasireotide monotherapy for at least 8 weeks at screening without achieving normal mUFC will enter the study with combination therapy with cabergoline. Cabergoline starting dose will be 0.5mg qd.

The stepwise approach implemented in the trial is consistent with clinical practice where patients are first started on monotherapy and, if necessary, combinations are considered.

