## 5 Patient population

The study population will consist of patients with persistent or recurrent Cushing's disease or patients with de novo Cushing's disease that are not considered candidates for pituitary surgery (poor surgery candidates, surgically unapproachable tumor, patients with no visible pituitary tumor, patients who refuse surgery). A confirmed Cushing's disease diagnosis is required.

The study will enroll a total of 64 patients.

The study population consists of patients who have never received pasireotide or patients who have received pasireotide sometime in the past but it was not discontinued because of safety. These patients will start pasireotide monotherapy at 0.6mg bid. In addition, patients who are currently treated with maximal tolerated doses of pasireotide monotherapy for at least 8 weeks at screening but with elevated muFC will enter the study with combination treatment of pasireotide at 0.3mg bid, 0.6mg bid, or 0.9mg bid, whichever the maximal tolerated dose they have reached, plus 0.5mg of cabergoline qd.

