### 5.1 Key inclusion criteria

1. Written informed consent obtained prior to any screening procedures.
2. Adult patients with confirmed diagnosis of ACTH-dependent Cushing's disease as evidenced by all of the following:
  - a. The mean of three 24-hour urine samples collected within 2 weeks  $> 1 \times \text{ULN}$  with 2 out of 3 samples  $> \text{ULN}$
  - b. Morning plasma ACTH within the normal or above normal range
  - c. Either MRI confirmation of pituitary adenoma  $> 6$  mm, or inferior petrosal sinus gradient  $> 3$  after CRH stimulation for those patients with a tumor less than or equal to 6 mm\*. For patients who have had prior pituitary surgery, histopathology confirming an ACTH staining adenoma
  - d. \*If IPSS had previously been performed without CRH (e.g. with DDAVP), then a central to peripheral pre-stimulation gradient  $> 2$  is required. If IPSS had not previously been performed, IPSS with CRH stimulation is required. If surgery has been performed and histopathology indicates an ACTH-secreting tumor, there is no need for IPSS even for patients with a tumor  $< 6$  mm. If surgery has not been performed and the tumor is  $< 6$  mm, IPSS is required to confirm the diagnosis using CRH, or DDAVP if CRH is not available.
3. Patients with de novo Cushing's disease can be included only if they are not considered candidates for pituitary surgery (e.g. poor surgical candidates, surgically unapproachable tumors, patients who refuse to have surgical treatment)
4. Male or female patients aged 18 years or greater
5. Karnofsky performance status  $\geq 60$  (i.e. requires occasional assistance, but is able to care for most of their personal needs)

6. Patients on medical treatment for Cushing's disease the following washout periods must be completed before screening assessments are performed
  - Inhibitors of steroidogenesis (ketoconazole, metyrapone): 1 week
  - Pituitary directed agents: Dopamine agonists (bromocriptine, cabergoline) and PPAR $\gamma$  agonists (rosiglitazone or pioglitazone): 4 weeks
  - Octreotide LAR, Lanreotide SR and Lanreotide autogel: 14 weeks
  - Octreotide (immediate release formulation): 1 week
  - Progesterone receptor antagonist (mifepristone): 4 weeks
7. Patients can be considered to enter the trial if they meet any one of the following criteria:
  - They are naïve to pasireotide

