  - They have received pasireotide in the past and have been discontinued because of lack of efficacy (2 weeks of washout prior to screening for patients treated with pasireotide subcutaneously and 12 weeks of washout prior to screening for patients treated with pasireotide LAR)
  - Patients who are on maximal tolerated dose but have not achieved biochemical control
8. Women of child-bearing potential, defined as all women physiologically capable of becoming pregnant, if they are using highly effective methods of contraception during dosing and for 30 days after stopping study medication. Highly effective contraception methods include:
  - Total abstinence (when this is in line with the preferred and usual lifestyle of the subject. Periodic abstinence (e.g., calendar, ovulation, symptothermal, post-ovulation methods) and withdrawal are not acceptable methods of contraception
  - Female sterilization (have had surgical bilateral oophorectomy with or without hysterectomy) or tubal ligation at least six weeks before taking study treatment. In case of oophorectomy alone, only when the reproductive status of the woman has been confirmed by follow up hormone level assessment
  - Male sterilization (at least 6 months prior to screening). For female subjects on the study the vasectomized male partner should be the sole partner for that subject.
  - Combination of any two of the following (a+b or a+c, or b+c):
    - a. Use of oral, injected or implanted hormonal methods of contraception or other forms of hormonal contraception that have comparable efficacy (failure rate <1%), for example hormone vaginal ring or transdermal hormone contraception.
    - b. Placement of an intrauterine device (IUD) or intrauterine system (IUS)
    - c. Barrier methods of contraception: Condom or Occlusive cap (diaphragm or cervical/vault caps) with spermicidal foam/gel/film/cream/vaginal suppository

In case of use of oral contraception women should have been stable on the same pill for a minimum of 3 months before taking study treatment.
9. Male participants in the trial must agree to use a condom during intercourse, and not to father a child during the study and for the period of 30 days following stopping of the study treatment.

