Patients who are currently treated with maximal tolerated doses of pasireotide monotherapy at 0.3mg, 0.6mg or 0.9mg twice a day for at least 8 weeks, but still with elevated UFC will immediately start the combination treatment by adding cabergoline 0.5mg once a day to their current pasireotide dose at study entry. Patients will continue with the combination treatment for 8 weeks. If biochemical control is not achieved by the end of the 8 weeks, the dose of cabergoline will be increased to 1mg once a day. At week 8, patients will continue to receive their starting combination dose until their UFC results are available, at which time, a decision will be made on whether to maintain the current dose or titrate up to the next combination dose.

All patients will be treated for a total of 35 weeks in the core phase.

The possible monotherapy or combination treatment regimens are as follows:

1. Monotherapy: pasireotide 0.3mg twice a day
2. Monotherapy: pasireotide 0.6mg twice a day
3. Monotherapy: pasireotide 0.9mg twice a day
4. Combination: pasireotide 0.3mg twice a day + cabergoline 0.5mg once a day
5. Combination: pasireotide 0.3mg twice a day + cabergoline 1.0mg once a day
6. Combination: pasireotide 0.6mg twice a day + cabergoline 0.5mg once a day
7. Combination: pasireotide 0.6mg twice a day + cabergoline 1.0mg once a day
8. Combination: pasireotide 0.9mg twice a day + cabergoline 0.5mg once a day
9. Combination: pasireotide 0.9mg twice a day + cabergoline 1.0mg once a day
10. Monotherapy: pasireotide 0.3mg once a day\*

\* This dosage should only be applied if a patient shows high sensitivity to pasireotide 0.6 mg bid resulting in cortisol values <LLN and/or signs/symptoms consistent with the diagnosis of hypocortisolism, the dose of pasireotide can be decreased to 0.3 mg bid. Despite the dose reduction, some patients may still present with cortisol values <LLN and/or signs/symptoms consistent with hypocortisolism; in this case the dose of pasireotide can be further reduced to 0.3 mg qd in order to achieve and maintain normal cortisol levels.

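### Protocol Section 6.7.1 drops the past-user limit from the pasireotide washout, so as written it conflicts with the entry route for patients currently on pasireotide s.c.

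*Protocol*

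**What the plan says.** **Section 6.7.1.** For patients on medical treatment for Cushing's disease, "the following washout periods must be completed before screening assessments are performed". Seven entries follow. Item 6 is "Pasireotide s.c.: 2 weeks" and item 7 gives 12 weeks for pasireotide LAR. Neither is limited to past users. The same section also prohibits, during the study, the drugs that appear in this washout list.

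**Section 5.1, criterion 6.** The lead-in is the same and so are the first five entries, but the list ends with "Progesterone receptor antagonist (mifepristone): 4 weeks". Pasireotide is not in it.

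**Section 5.1, criterion 7.** Three alternative ways to qualify are given. Patients who received pasireotide before and stopped for lack of efficacy need "2 weeks of washout prior to screening for patients treated with pasireotide subcutaneously" (12 weeks for LAR). A separate alternative, with no washout attached, is "Patients who are on maximal tolerated dose but have not achieved biochemical control".

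**The currently treated route elsewhere.** Section 5 describes patients "currently treated with maximal tolerated doses of pasireotide monotherapy for at least 8 weeks at screening but with elevated muFC". Section 2.2 describes "pasireotide-treated patients who at the time of screening have not achieved biochemical control despite maximal tolerated doses of pasireotide for at least 8 weeks". Section 6.2 says they "will immediately start the combination treatment by adding cabergoline 0.5mg once a day to their current pasireotide dose at study entry". Sections 4.1 and 6.4.1 give the same route, with pasireotide doses of 0.3, 0.6 or 0.9 mg twice a day.

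**The concern.** A patient cannot have been off pasireotide s.c. for two weeks before screening and also be currently treated with it, for at least 8 weeks, at screening. Section 6.7.1 demands the first and the route demands the second. Both are current operative text, and no rule says which section takes precedence.

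A site that followed 6.7.1 to the letter would take the patient out of the currently treated route. The patient might then not be enrolled at all: criterion 7's past-user alternative requires stopping for lack of efficacy, which stopping only to complete a washout may not satisfy. Otherwise the patient would enter as pasireotide-untreated, restart 0.6 mg bid monotherapy and wait for cabergoline. That start would apply even to someone whose maximal tolerated dose had been 0.3 mg bid, which the route allows.

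Conversely, a site that enrolled such a patient as Section 5.1 intends would breach the wording of 6.7.1, in a protocol whose Section 12 permits no authorised deviations.

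**Working it through.** The plan gives no figure on this point. The check compares the texts and then works out the timing.

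**1. Comparison of the provisions (Protocol)**

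| Provision | Who it covers | Pasireotide s.c. before screening |
|---|---|---|
| 6.7.1 item 6 | all patients on medical treatment | off for 2 weeks |
| 5.1 criterion 6 | all patients on medical treatment | not listed |
| 5.1 criterion 7, past users | stopped for lack of efficacy | off for 2 weeks |
| 5.1 criterion 7, maximal tolerated dose | currently treated | no washout |
| 2.2 and 5 | currently treated | on drug for at least 8 weeks at screening |
| 6.2 | currently treated | cabergoline added to the current dose at entry |

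The first row conflicts with the last three. Items 6 and 7 of 6.7.1 carry exactly the two washouts of criterion 7 (2 and 12 weeks), appended to the five entries of criterion 6. The natural reading is that the two criteria were merged and the past-user clause was lost, so 6.7.1 is the place in error. Item 7 lost the same clause but does not conflict with this route, whose twice-daily doses are the s.c. regimen.

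**2. Number of patients in the route**

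- Planning maximum (Section 10.5): 6 / 64 = 9.4%.
- Entered at Amendment 2: 2 / 52 = 3.8%.

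The first is a planning ceiling for the whole route and the second an enrolment count. Neither counts patients affected.

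**3. Start of cabergoline if the patient restarted as untreated**

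Inputs: 8-week dose periods and 1-week titration periods (Section 4.1), and the dose steps in Section 6.4.1 and Table 6-2. The core phase is 35 weeks.

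- Currently treated route: week 0, so 35 weeks of combination by week 35.
- 0.6 mg bid with no increase possible: 8 + 1 = week 9, leaving 35 − 9 = 26 weeks.
- Standard sequence through 0.9 mg bid: 8 + 1 + 8 + 1 = week 18, leaving 35 − 18 = 17 weeks.
- Step-down to 0.3 mg bid after *t* weeks: at least 8 weeks are needed at 0.3 mg bid before cabergoline. Assuming one titration week, *t* + 8 + 1 = week 9 + *t*.
- 0.6 to 0.9 and back to 0.6 mg bid (Table 6-2, Modification 3): with *t* weeks at 0.9 mg, and assuming a further 8 weeks at 0.6 mg and one titration week, 9 + *t* + 8 + 1 = week 18 + *t*.

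Each titration period may also run up to 3 days longer. Weeks 9 and 18 are therefore reference points, and 17 weeks is not the least combination time possible.

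**4. Primary criterion**

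Section 10.2.2 counts patients with mUFC at or below 1.0 × ULN at week 35. Baseline mUFC does not enter.

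**The case against.** The strongest reply is that the protocol resolves the conflict itself. Eligibility belongs to Section 5.1, criterion 7 is explicit, and Section 7.1.1.1 requires an eligibility checklist before the first dose. Several other sections describe the currently treated route consistently. This stands, and it is why the point ranks low.

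A second reply is that 6.7.1 cannot be meant literally. It also prohibits the listed washout drugs during the study, and the list contains pasireotide s.c. and cabergoline, so a literal reading would ban both study treatments for everyone. This also stands as evidence of intent. It shows a further sentence that needs an exemption, though, rather than a reason to leave item 6 alone.

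Third, item 6 acts only before screening, and Amendment 4 reports that results from the core-phase interim analysis were already available. Screening was therefore probably over, and an edit to this version may change no patient's handling. That is a fair inference. What remains is to make clear that absence of washout in this route is not a deviation.

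Fourth, patients did enter by the route: 2 of 52 at Amendment 2, and SAP Section 6.3 summarises Group 2's prior pasireotide duration. The route was evidently not closed, although the documents do not say how washout was handled.

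A reader might also infer that the washout gave currently treated patients an off-drug baseline mUFC, distorting change from baseline, the 50% reduction rate, duration of response or the baseline categories. The documents do not support this. A patient who had washed out would not be currently treated at screening and so would no longer belong to the route. As an untreated entrant, the patient would have an off-drug baseline by design.

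**Conclusion.** Section 6.7.1 is wrong as written: items 6 and 7 lack the past-user limit of criterion 7, and item 6 is incompatible with the currently treated route. The route's planning maximum is 6 of 64 patients (9.4%). Taken literally, the rule would cost such a patient enrolment, or would delay cabergoline from week 0 to about week 9 at the earliest where 0.9 mg bid is not possible, to about week 18 by the standard sequence, and possibly later on other titration paths. These timings assume entry as pasireotide-untreated and the 8-week and 1-week periods of Section 4.1.

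Nothing shows that any patient was washed out, turned away or moved between routes, so it would go too far to say that enrolment or the results were affected. The definition of the primary criterion is untouched, the trial is exploratory with no formal hypothesis testing, and the intended rule can be read from Section 5.1. The point sits at the bottom of the minor range.

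**What to change.** Three edits to Section 6.7.1:

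1. Limit items 6 and 7 to patients who previously received and discontinued pasireotide, as in inclusion criterion 7.
2. State that patients entering on maximal tolerated pasireotide s.c. continue it without washout.
3. Exempt pasireotide and cabergoline given as study treatment from the sentence that prohibits the listed washout drugs during the study.

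The cost is a few words of text, with no added visits, patients, outputs or analyses. If screening is already closed, a short clarification that absence of washout in the currently treated route is not a deviation would serve the same purpose.
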